All participants will complete a comprehensive AI-literacy training program covering LLM capabilities, limitations, prompt engineering techniques, and output evaluation strategies before beginning the trial. Responses will be evaluated by blinded reviewers using an expert-developed assessment rubric specifically designed to detect uncritical acceptance of erroneous information. This naturalistic approach will yield insights directly applicable to real clinical workflows, where increasing cognitive demands can progressively impact diagnostic decision quality, while providing evidence on scalable interventions to preserve clinical judgment in AI-augmented diagnostic settings.

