2.3 Sample Size and Power Analysis

Target Sample Size: 50 participants (25 per arm).

Power Calculation: Based on pilot data and similar studies, we assume:

- An effect size (difference in mean diagnostic reasoning scores) of 8 percentage points between groups.
- A standard deviation of 16.2%.
- An intraclass correlation coefficient (ICC) between 0.05 and 0.15 (to account for clustering of cases within participants).
- An average of 4 completed cases per participant.

With these assumptions, a sample size of 50 provides $\geq 80\%$ power to detect a significant difference in the primary outcome, diagnostic reasoning score, between the two groups using a linear mixed-effects model ($\alpha = 0.05$, two-sided).

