2.4 Clinical Vignettes & LLM Recommendations

Participants will evaluate six clinical vignettes specifically designed to measure automation bias. These vignettes will:

- Be based on modified real cases.
- Represent a range of diagnostic complexity across common medical specialties.
- Avoid overly simplistic or extremely rare conditions.
- Follow a standardized format, including:
 - Chief complaint and history of present illness.
 - Relevant past medical, social, and family history.
 - Physical examination findings.
 - Initial laboratory results.
- Include three clinical vignettes whose LLM recommendations contain deliberately introduced clinical reasoning errors and three with accurate recommendations, presented in randomized order. A panel of three licensed physicians will design these errors to be subtle yet clinically significant and detectable by trained clinicians.

- For every vignette, the LLM's recommendations will be pre-generated and fixed. This ensures all participants see identical recommendations for each vignette, the same error in flawed cases and the same correct reasoning in accurate cases, eliminating variance from real-time model variability.

Vignette Selection and Validation:

- A pool of 10 potential vignettes will be created and reviewed by an independent panel of three experienced medical doctors for:
 - Clinical accuracy and realism.
 - Appropriateness of difficulty level.
 - Clarity and completeness of information.
 - In flawed vignettes: subtlety and clinical significance of the introduced errors (errors should be detectable by competent physicians but not immediately obvious).
- Six vignettes will be selected based on the panel's ratings and feedback, aiming for a balanced representation of medical specialties and diagnostic challenges.
- For intervention arm participants, LLM output will be pre-generated and standardized for each vignette to ensure consistency in the presentation of correct or flawed information.

Vignette Completion:

- Each participant will complete all six vignettes in a single, proctored, approximately 75-minute session.
- The order of vignettes will be randomized for each participant to control for order effects and prevent pattern recognition.

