4.2 Primary Outcome Analysis

- A linear mixed-effects model will be used to compare the mean diagnostic reasoning accuracy score between the intervention and control groups.
- **Model Structure:**
 - **Dependent Variable:** Diagnostic reasoning performance score (percentage).
 - **Fixed Effect:** Treatment group (Intervention vs. Control).
 - **Random Effects:**
 - * Participant ID (to account for within-participant correlation across cases).
 - * Vignette ID (to account for potential variability in case difficulty).
 - **Covariates:**
 - * Years of practice post MBBS, gender, and prior experience with LLMs.
- **Primary Comparison:** The difference in mean diagnostic reasoning scores between the two groups, adjusted for random effects and covariates.
- **Significance Threshold:** A two-sided p-value ≤ 0.05 will be considered statistically significant.

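### Vignette order is randomised but sequence position enters no model; if the arms complete different numbers of vignettes, drift within the session could bias the arm contrast modestly, in either direction

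*Combined protocol and SAP*

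**What the plan says.** **Order.** Section 2.4: "The order of vignettes will be randomized for each participant to control for order effects and prevent pattern recognition". The plan therefore recognises that order effects are possible. It gives them no direction and no size.

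**Model.** Section 4.2 has a fixed effect of arm, random effects for participant and vignette, and these covariates: "Years of practice post MBBS, gender, and prior experience with LLMs". The vignette effect is there for case difficulty. Section 4.3 reuses the same random effects for top-choice accuracy. Neither the sensitivity analyses (4.5) nor the exploratory analyses (4.6) bring in position. Section 2.5.1 records time per vignette and whether the LLM panel was opened; it does not list sequence position.

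**Completion.** Section 2.4 has every participant finish all six vignettes in one proctored session of about 75 minutes. The power assumptions in section 2.3 include "An average of 4 completed cases per participant". Section 4.7 bases the primary analysis on complete cases, without saying whether a case is a vignette or a participant. Section 4.5 repeats the analysis with incomplete cases and offers multiple imputation as an example.

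**Change over time.** The Introduction refers to real clinical workflows, "where increasing cognitive demands can progressively impact diagnostic decision quality".

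**The concern.** Randomising order makes position independent of arm at the moment of assignment. It does not keep the positions that are finally scored balanced if the arms finish different numbers of vignettes. Vignettes are presented one at a time, so those left undone for lack of time would be the last. The number completed is also a post-randomisation quantity that the nudge could change: it is meant to prompt slower, more deliberate reasoning, and section 4.6 reads longer time on Red-signal vignettes as a sign of this. Six vignettes in about 75 minutes is 12.5 minutes each.

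If one arm is scored on earlier positions and performance drifts through the session, the drift is counted as treatment effect. The vignette random effect cannot absorb it, because under random order each vignette appears at every position. Imputing late vignettes from a model without position would not help either: it would fill them with early-position performance.

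**Working it through.** **Inputs from section 2.3.** 25 participants per arm; "An effect size (difference in mean diagnostic reasoning scores) of 8 percentage points between groups"; "A standard deviation of 16.2" percent; "An intraclass correlation coefficient (ICC) between 0.05 and 0.15"; 4 completed cases each; two-sided alpha 0.05.

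**Step 1: the plan's own figure.** Effective observations per arm = 25 × 4 / (1 + 3 × ICC), and SE = 16.2 × √(2 / effective n).

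| ICC | effective n per arm | SE | power (normal) | power (t, 48 df) |
|---|---|---|---|---|
| 0.05 | 100/1.15 = 86.96 | 2.457 | 90.3% | 89.1% |
| 0.10 | 100/1.30 = 76.92 | 2.612 | 86.5% | 85.1% |
| 0.15 | 100/1.45 = 68.97 | 2.759 | 82.6% | 81.1% |

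The stated power of at least 80% reproduces with 16.2 as a per-case SD. Read as a participant-level SD it would give 41.5%.

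**Step 2: size of the bias.** Let b be the change in score per position, and let kT and kC be the numbers completed in the intervention and control arms. If the first k vignettes are the ones completed, their mean position is (k + 1)/2. Without a position term, then:

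bias = b × [(kT + 1)/2 − (kC + 1)/2] = b × (kT − kC)/2.

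The documents give neither b nor the gap, so both are assumed over a range. A positive bias favours the intervention.

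| b per position | equal completion | intervention one fewer | intervention two fewer |
|---|---|---|---|
| −1 | 0 | +0.5 | +1.0 |
| −2 | 0 | +1.0 | +2.0 |
| −3 | 0 | +1.5 | +3.0 |
| +2 (practice gain) | 0 | −1.0 | −2.0 |

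The equal-completion column is the same at 4 versus 4 and at 6 versus 6. Against the 8-point target, a one-vignette gap with falls of 1, 2 and 3 points gives 0.5/8 = 6%, 1.0/8 = 12.5% and 1.5/8 = 19%.

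**Step 3: simulation check.** The participant-plus-vignette model was fitted by generalised least squares with known variance components, 10% of variance assumed to lie between vignettes, no baseline covariates, 600 null trials per setting, and ICC 0.05 and 0.15.

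- Without position, one fewer vignette (3.5 versus 4.5): bias +0.55 and +0.62 for a fall of 1 point, and +1.53 and +1.36 for a fall of 3. These agree with the formula.
- Type I error without position, fall of 1 point: 6% to 7% with one fewer, 5% to 8% with two fewer. Fall of 3 points: about 10% with one fewer, 22% to 30% with two fewer.
- With a linear position term, bias was within about 0.3 points of zero and type I error was 4% to 8%. The simulation error on a 5% rate is √(0.05 × 0.95/600), about 0.9 percentage points.

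**Step 4: cost of the term at ICC 0.15, fitted as linear.**

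| completed (intervention vs control) | SE without | SE with |
|---|---|---|
| 6 vs 6 | 2.40 | 2.40 |
| 4 vs 4 | 2.67 | 2.67 |
| 3.5 vs 4.5 | 2.69 | 2.72 |
| 4 vs 6 | 2.54 | 2.61 |
| 3 vs 5 | 2.72 | 2.84 |

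Simulated power at 8 points, with the term and unequal completion, ran from 78.5% to 94.5% over both ICCs (200 runs per setting).

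**The case against.** The strongest reply is that section 2.4 has every participant complete all six vignettes. If that holds, position is balanced within each person, the bias is zero at any drift, and the term changes nothing. The average of 4 appears only as a power assumption. This stands, and it makes the problem conditional. It does not close the matter, because the two sections disagree and nothing says which will describe the data.

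A reader might infer that incomplete sessions alone defeat the random order. They do not: 4 versus 4 is as safe as 6 versus 6. Only a difference between arms matters, and the documents neither give nor predict completion by arm.

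A reader might also infer that the plan expects performance to decline during the session. The Introduction's clause concerns real workflows and says only that quality can be affected; it forecasts nothing for these 75 minutes. Nor does it follow that the arm completing fewer vignettes will look better. If scores rise with familiarity with the form and platform, the sign reverses.

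Three further limits stand. No hard time cut-off is stated, so it is an assumption that the unfinished vignettes are the last ones. The nudge is seen only when the LLM panel is opened, and the planned timing comparison is within the intervention arm, so a between-arm slowing is inferred. And if complete cases means participants with all six vignettes, position balances and a selection problem takes its place, which a position term would not repair.

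**Conclusion.** The point holds as a conditional one. Position is absent from every planned model, and the primary contrast is exposed to drift if four things coincide: complete cases means completed vignettes, the unfinished ones are the last, the arms differ in number completed, and scores drift with position. For a one-vignette gap and 1 to 3 points of drift per position, the bias is 0.5 to 1.5 points, in a direction that depends on whether scores fall or rise. At 1.0 point it is about 0.4 of a standard error (1.0/2.69). Serious inflation of type I error needs a two-vignette gap together with steep drift. The drift and the gap are assumptions throughout.

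The documents do not support saying that the planned analysis is biased as it stands, or that it is tilted towards the nudge. This is a cheap improvement of low to moderate priority, worth making because it guards in both directions and costs nothing when completion is equal.

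**What to change.** 1. Export each vignette's sequence position (1 to 6) from the platform and list it among the recorded data in section 2.5.1.
2. Prespecify position as a six-level factor, as a fixed effect, in the 4.2 and 4.3 models.
3. Add it to the score and time comparisons in 4.6, where the gain is mainly precision.
4. Include position in any imputation model used under 4.5 or 4.7.
5. Report the number of vignettes completed by arm.
6. Reconcile six completed (2.4) with an average of 4 (2.3), and state in 4.7 whether complete cases refers to vignettes or participants.

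**Cost.** One exported variable and at most five degrees of freedom out of 50 × 4 = 200 to 50 × 6 = 300 rows. With equal completion the SE does not change. With a one-vignette gap, the linear term raised it from 2.69 to 2.72, about 1%. A factor costs slightly more than a linear term when the gap is wide, because the latest positions are then seen in one arm only and add little to the contrast; in exchange it assumes no shape for the drift. It should be settled before data are seen, since section 6 would treat a later addition as a deviation to be justified.

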4.3 Secondary Outcome Analyses

- **Top Choice Diagnosis Accuracy:**

- A linear mixed-effects model will be used, with the same random effects structure as the primary analysis, and the dependent variable being the top choice diagnosis accuracy.

4.4 Subgroup Analyses

Subgroup analyses will be performed to explore whether the effect of the intervention differs among physicians based on physician experience level (e.g., years since MBBS/MD), gender, and prior LLM experience.

4.5 Sensitivity Analyses

The following sensitivity analyses will be conducted to assess the robustness of the findings:

- **Incomplete Cases:** The primary outcome analysis will be repeated including incomplete cases (if any) to evaluate the potential impact of missing data (e.g., using multiple imputation).
- **Scorer Agreement:** Inter-rater reliability for the diagnostic reasoning scores across at least two raters will be assessed using Cohen's kappa or Fleiss' kappa depending on the final number of raters.
- **Internal Consistency:** The internal consistency of the diagnostic reasoning score across the six vignettes will be assessed using Cronbach's alpha.
- **Distribution Analysis:** Assessment of normality assumptions through:
 - Visual inspection of distributions (e.g., Q-Q plots, histograms)
 - Formal tests of normality (e.g., Shapiro-Wilk test)

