3.1 Primary Outcome

Diagnostic Reasoning Accuracy Score: This will be a composite score (expressed as a percentage) based on a structured rubric that evaluates the following components for each clinical vignette:

1. **Quality of Differential Diagnoses:** (0-3 points)
 - 0: No reasonable differential diagnoses listed.
 - 1: One reasonable differential diagnosis listed.
 - 2: Two reasonable differential diagnoses listed.
 - 3: Three or more reasonable differential diagnoses listed, including the correct diagnosis.
2. **Supporting Findings:** (0-1 points per diagnosis)
 - 0: No relevant supporting findings listed.
 - 1: Some relevant supporting findings listed, but incomplete.
 - 2: Comprehensive list of relevant supporting findings.
3. **Opposing Findings:** (0-1 points per diagnosis)
 - 0: No relevant opposing findings listed.
 - 1: Some relevant opposing findings listed, but incomplete.
 - 2: Comprehensive list of relevant opposing findings.
4. **Top Choice Diagnosis Accuracy:** (0-18 points)
 - 0: Incorrect final diagnosis.
 - 9: Partially correct final diagnosis (e.g., correct category but wrong specific diagnosis).
 - 18: Correct final diagnosis.
5. **Appropriateness of Next Steps:** (0-1 points per step)
 - 0: Inappropriate or unnecessary next steps.
 - 0.5: Partially appropriate next steps (e.g., some necessary tests missing).
 - 1: Appropriate and comprehensive next steps.

The total score for each vignette will be the sum of these components.

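### Rater agreement on the percentage score is to be measured with unweighted kappa, which treats a half-point difference like a 9-point one, so the reported reliability will mislead

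*Combined protocol and SAP*

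**What the plan says.** Section 4.5, under Scorer Agreement, states: "Inter-rater reliability for the diagnostic reasoning scores across at least two raters will be assessed using Cohen's kappa or Fleiss' kappa", the choice between the two being made "depending on the final number of raters". It gives no weights, no grouping of the score into bands, no agreement analysis by rubric component, no ICC or limits of agreement, and no acceptability threshold.

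The quantity being rated is set out in section 3.1: "This will be a composite score (expressed as a percentage) based on a structured rubric". It adds: "The total score for each vignette will be the sum of these components". The components move in steps of 0.5 (next steps), 1 (differentials and findings) and 9 (final diagnosis, scored 0, 9 or 18). Section 4.2 enters the resulting percentage as the dependent variable of a linear mixed-effects model.

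**The concern.** The plan treats the same score as continuous when it estimates the treatment effect and as a set of unordered labels when it assesses whether raters agree. The number of raters decides which kappa is used; the scale of the score plays no part.

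Unweighted kappa can mislead in two directions. Good scoring can look poor, because two careful raters will seldom land on exactly the same total. A middling kappa can also hide serious disagreement, because it does not separate a half-point difference on one next step from a difference that moves the final-diagnosis item by a full level. The primary outcome is scored by people from written responses, so a reader will use this figure to judge whether the outcome can be trusted.

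**Working it through.** The plan states no kappa value or target, so there is no figure to reproduce. The check is from definitions, then by simulation.

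**Inputs**
- Scored responses: 50 participants (2.3) × 6 vignettes (2.4) = 300.
- Score steps: 0.5, 1 and 9 points (3.1).
- SD 16.2% and target difference 8 percentage points (2.3).
- Maximum score: not stated. Section 3.1 caps findings at 1 point per diagnosis but lists levels up to 2, and gives no number of next steps. Assuming three next steps, the maximum is 3 + 3 + 3 + 18 + 3 = 30, or 3 + 6 + 6 + 18 + 3 = 36.

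**Number of categories.** In half-point steps there are 30/0.5 + 1 = 61 possible totals, or 36/0.5 + 1 = 73.

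**What kappa sees.** Kappa = (p_o − p_e)/(1 − p_e), where p_o is the proportion of exact matches and p_e the proportion expected by chance. The size of a mismatch appears nowhere. If 40% of responses differ, p_o = 0.60. With p_e about 0.03 (the value the simulated kappas imply), kappa = 0.57/0.97 = 0.588. Simulation gave 0.588 for half-point and 0.589 for 9-point differences. In percentage points these are 0.5/36 = 1.4 to 0.5/30 = 1.7, against 9/36 = 25 to 9/30 = 30.

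**What the ICC sees.** With no mean shift between two raters, ICC ≈ covariance / average variance. On 30 points the SD is 0.162 × 30 = 4.86 and the variance 23.62. Let the second rater differ on 40% of responses, up or down at random:
- by 0.5 point: added variance 0.4 × 0.25 = 0.10; ICC ≈ 23.62/(23.62 + 0.05) = 0.998;
- by 9 points: added variance 0.4 × 81 = 32.4; ICC ≈ 23.62/(23.62 + 16.2) = 0.59.

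Simulations under different assumptions, including the direction of the 9-point differences, gave 0.37 to 0.71 for the second case and above 0.99 for the first.

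**Frequency held equal, size varied** (500 sets of 300 responses, assumed component distributions, 36-point maximum)

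| Responses differing | Kappa, 0.5 point | Kappa, 9 points | ICC, 0.5 point | ICC, 9 points |
|---|---|---|---|---|
| 25% | 0.74 | 0.74 | >0.99 | 0.83 |
| 50% | 0.49 | 0.49 | >0.99 | 0.63 |
| 75% | 0.23 | 0.23 | >0.99 | 0.39 |

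Fleiss' kappa agreed with Cohen's to within 0.01.

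**Random rater error on the total** (200 sets of 300, 30-point scale, true-score SD 4.86, two raters, rounded to 0.5)

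| Error SD (points) | Kappa | ICC |
|---|---|---|
| 0.5 | 0.25 | 0.99 |
| 1.0 | 0.12 | 0.96 |
| 1.5 | 0.07 | 0.91 |
| 2.0 | 0.05 | 0.85 |

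The ICC column agrees with theory: at SD 1, 23.62/(23.62 + 1) = 0.96.

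**Errors on individual rubric items** (300 sets of 300, 36-point maximum, each rater independently one level off)

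| Error rate, small items / final diagnosis | Exact agreement | Kappa | ICC |
|---|---|---|---|
| 5% / 2% | 50% | 0.49 | 0.98 |
| 10% / 2% | 30% | 0.29 | 0.98 |
| 20% / 5% | 16% | 0.13 | 0.95 |
| 30% / 5% | 11% | 0.09 | 0.94 |

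Three raters with Fleiss' kappa gave the same pattern (0.49 down to 0.09). In these runs quadratic-weighted Cohen's kappa matched the ICC.

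**The case against.** **Weights may be intended.** The text does not say unweighted, and quadratic weights would largely cure the problem. This does not rescue the plan as written: no weights are named, and standard Fleiss' kappa, which applies with three or more raters, has none.

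**Kappa may be meant for the components.** The rubric items are ordered categories, where weighted kappa is reasonable. But section 4.5 applies kappa to the diagnostic reasoning scores and does not mention components.

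**The sizes are scenario-dependent.** This stands. The 30-point maximum is assumed, 16.2% is used as the SD of true scores, and normally distributed error on the total makes exact matches rarer than rubric scoring may. With only 1% error per item on a 30-point scale, kappa was 0.80 against an ICC of 0.98; at 2%, 0.64 against 0.97. The gap narrows with very accurate raters but keeps its direction.

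**Cronbach's alpha is also planned.** True, and random scoring error lowers it, but it measures consistency across vignettes. Kappa is therefore the only inter-rater check, not the only reliability statistic.

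**An ICC on the total has its own blind spot.** The diagnosis item supplies 18 of 30 or 36 points. With raters wrong on half of all the small items but agreeing fully on the diagnosis, a simulated total-score ICC was still 0.96. That correctly describes the total the trial analyses, but it is a good reason to report components as well.

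**Stakes are limited.** This also stands: no threshold, rescoring rule or model term depends on kappa.

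**Conclusion.** The concern holds. Section 4.5 names a statistic for unordered categories and applies it to a numeric score, so the reliability it reports will not describe how closely raters agree. The usual distortion is understatement: kappa of about 0.05 to 0.5 in most simulated settings where the ICC was 0.85 to 0.99. Kappa also cannot reveal disagreements of 25 to 30 percentage points, more than three times the 8-point difference the trial is powered to detect (25/8 = 3.1).

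These sizes rest on the assumed maximum score, score distributions and rater error rates. That disagreement size is ignored rests on the definition of kappa alone. The treatment estimate and its p-value are unchanged, so this should be corrected but does not threaten the primary comparison.

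**What to change.** In section 4.5, replace kappa for the diagnostic reasoning score with a two-way random-effects, absolute-agreement ICC with 95% CI, calculated on the raters' independent vignette-level scores. It serves two or more raters. State whether the single-rater or the average-rater form is reported, to match how several raters' scores are combined for analysis, which the plan does not say.

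Use weighted kappa, with the weights named, for the ordered 0/9/18 final-diagnosis item. A short table of agreement on the remaining components, or limits of agreement for the percentage score, would be a useful addition.

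The cost is a line or two of SAP wording, with the same raters and the same ratings. The change should be made before scoring starts: switching statistic after a poor kappa has been seen would look like a post hoc choice.
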